8.1.2.1.4 Unexpected Adverse Drug Reactions (ADRs)

Unexpected ADR refers to an adverse drug reaction that differs in its pattern or severity of harm compared to the information of the investigational drug (refer to the investigator's data sheet).

This includes delayed events such as anaphylaxis or allergic reactions related to vaccine administration, and unexplained neurological events.

8.1.2.1.5 Evaluation of adverse events

All items identified for the adverse reaction, such as occurrence, symptom, date of onset, date of disappearance, severity, relationship with the investigational drug, related measures, treatment, and results, should be recorded in the e-CRF.

Abnormal values of laboratory tests that are considered clinically significant, vital signs, and abnormal findings of ECG results are recorded as adverse reactions.

8.1.2.1.6 Assessing Severity (Intensity)

The Investigator will grade laboratory AEs and clinical AEs (based on discussions with study participants) using the Toxicity Grading Scale for Healthy Adult and Adolescent Volunteers Enrolled in Preventive Vaccine Clinical Trials (Appendix A):

Adverse events will be recorded on the eCRF at the severity reported by the Investigator.

- Mild (Grade 1)
- Moderate (Grade 2)
- Severe (Grade 3)
- Potentially Life Threatening (Grade 4)

8.1.2.1.7 Causal Relationship of Clinical Material to Adverse Events

A causally related AE is one judged to have a suspected relationship to the administration of the investigational agent. Conversely, an AE may also be assessed as not related to the investigational product. The Investigator is responsible for reporting adverse events and judging the relationship between the administration of the investigational product and an AE because the investigator is knowledgeable about the participant (e.g., medical history, concomitant medications), administers the investigational product, and monitors the participant's response to the investigational product. The Sponsor will assess the overall safety of the investigational product and determine whether expedited reporting to regulatory agencies is indicated.

Investigators should use their knowledge of the Study Participant, the circumstances surrounding the event, and an evaluation of any potential alternative causes to determine whether or not an adverse event is considered to be related to the study drug by the following criteria:

- Related – the Investigator considers that there is a causal relationship between the event and study drug;
- Probably related – the Investigator considers that there is a probability of a causal relationship of the event to the study drug
- Possibly related – the Investigator considers that there is a possible causal relationship of the event to the study drug
- Not related – the Investigator considers that the event has no relationship to administration of the study drug

The following guidance should also be taken into consideration:

- Temporal relationship of event to initiation of study drug;
- Course of the event, discontinuation of study drug, or reintroduction of study drug (when applicable);
- Known association of the event with the study drug or with similar treatments;
- Known association of the event with the disease under study (as applicable);

- Presence of risk factors in the Study Participant or use of concomitant medications known to increase the occurrence of the event

8.1.2.1.8 Measures related to investigational products

Any of the following measures with regard to investigational product dosing during the study if adverse events, abnormal laboratory values occur or in response to immunologic assessments:

- 1) Maintain the study drug dose
- 2) Increase the study drug dose
- 3) Decrease the study drug dose
- 4) Cessation of administration of study drug
- 5) Not applicable

8.1.2.1.9 Treatment for adverse Events

Any of the following treatment measures that may be implemented during the study related to adverse events should be documented:

- 1) Treatment with medication therapies
- 2) Treatment with non-medication therapies
- 3) Treatment with both medication and non-medication therapies
- 4) No treatment

8.1.2.1.10 Consequences of adverse Events

Any of the following consequences of abnormal events may occur and should be documented:

- 1) Recovered
- 2) Recovering
- 3) Not Recovered
- 4) Recovered, but after-effects remain
- 5) Death
- 6) Unknown

8.1.3 Physical Assessments and Targeted Physical Assessment

A complete physical examination will be performed at study enrollment. Targeted physical examinations based on symptoms will be performed at subsequent visits based on participant complaints.

8.1.4 Vital Signs

Participant vital signs will be performed and recorded at all study visits.

8.1.5 Safety Laboratory Evaluations

Blood for a complete blood count with differential(RBC, hemoglobin, hematocrit, platelet, WBC, neutrophil, lymphocyte, monocyte, eosinophil, basophil) and chemistries (consisting of sodium, potassium, blood urea nitrogen (BUN), creatinine, glucose, ALT, and bilirubin, Ca, Cl, AST, ALP, CPK, albumin, total protein, total cholesterol) will be performed at Visits 1, 2, 4 and 8. A urine pregnancy test will be performed at Visit 1 and Visit 3 for those of childbearing potential. Laboratory test abnormalities are generally not recorded as adverse events or serious adverse

events. According to the judgment of the investigator, a clinically significant abnormal value is reported as an adverse event, and if it is related to a clinical adverse event, it is reported as the name of the adverse event. For laboratory test results, normal/abnormal evaluation is performed according to the normal range of the clinical trial site, and the severity is evaluated by the Toxicity Grading Scale.

8.1.6 Procedures for Documenting Pregnancy During Study

Women of childbearing potential who are pregnant or expect to become pregnant within 4 weeks from the boost vaccination, or who cannot agree to use an approved form of birth control will be excluded from participation in the study. Approved forms of pregnancy prevention are as follows,

- ① Hormonal contraceptives (e.g., oral progesterone single or estrogen-progesterone complex, transdermal delivery type contraceptives, depot injections, etc.)
- ② Implantation of intrauterine devices or intrauterine systems
- ③ Double blocking method [male physical blocking method (eg. male condom) and female physical blocking method (eg. cervix cap, contraceptive diaphragm, contraceptive sponge) are used in combination, and spermicide is used together. The use of condoms in all cases is not recommended as damage from physical friction may be less effective than expected contraception.]
- ④ Surgery and operation status such as tubal ligation (resection), hysterectomy, and vasectomy (resection)

Approved birth control methods include use of pills or injections of hormones to prevent pregnancy, use of a male or female condom with or without use of a spermicidal cream or gel, use of a diaphragm or cervical cap with concomitant use of a spermicidal cream or gel, IUD, or sexual abstinence. Should a participant become pregnant after enrolling in the study, she will not be given any further study treatment.

Participants who become pregnant at any point during the study will continue to be followed for clinical safety assessments without receiving further investigational product. The Investigator will report any pregnancies to the study team and medical monitor (or designee), and to the Investigational Review Board (IRB). Sites should request the participant's permission to follow the outcome of the pregnancy documenting such in the clinical study report.

Subjects whose pregnancy is confirmed during the clinical trial period are followed up for safety evaluation with the vaccination of the investigational product discontinued. The decision regarding collection of safety and/or immunology labs will be deferred to the PI.

If the participant does not wish to continue in the study and complete safety measurements, they will be listed as having withdrawn voluntarily.

8.1.7 Post-study Reporting Requirements

SAEs, including deaths, regardless of cause or relationship, must be reported to Sponsor at the time that such events become known to the Investigator.

Investigators are not obligated to actively seek AEs or SAEs beyond the follow up period for participants. However, if the Investigator learns of an SAE that occurs within 30 days from

completion or termination visit, the Investigator should promptly document and report the event to the study team and medical monitor.

8.2 Methods and Timing for Collection and Recording of Safety Data

At the time of each study visit, participants will be queried as to adverse events that have occurred in the interim period and the current status of any AE that was reported at a prior visit that has not yet resolved. Additionally, labs will be reviewed for safety.

All AEs, regardless of severity, seriousness, or presumed relationship to study treatment, must be recorded using medical terminology in source documents and on the eCRF. Whenever possible, a diagnosis will be documented, in lieu of symptoms. The source document and the eCRF must contain the Investigator's opinion concerning the relationship of the AE to study treatment.

AEs should be described with the following attributes:

- Duration (start and end dates)
- Seriousness
- Severity
- Causality
- Action(s) taken
- Outcome

8.3 Safety and Toxicity Management

The Medical Monitor will be responsible for the overall safety monitoring of the study. The site PI will be responsible locally for safety.

Safety assessments include the following:

- Incidence of all adverse events classified by system organ class (SOC), preferred term, severity, and relationship to study treatment
- Changes in safety laboratory parameters
- Other clinically significant changes in safety evaluations

Local and systemic injection site review; special attention will be paid to the examination of the injection site. Administration site reactions and the participant's complaints will be documented.

8.3.1 Events Requiring Expedited Reporting

Events requiring expedited reporting (ERER) are defined as any Adverse Events including:

- Grade 3 or greater systemic or local symptoms;
- Grade 3 or greater laboratory abnormalities
- Any episode of anaphylaxis or allergic reaction considered as study drug related or possibly study drug related

Sites will inform the Sponsor of any ERER within 24 hours, or increase of severity of an adverse event to Grade 3, to discuss whether dosing to the participant should continue.

8.3.2 Stopping Rules

If any of the following situations occur, then further enrollment and Study Treatments will be halted immediately until a thorough investigation has been conducted by the Medical Monitor and PI and the IRB (if applicable):

- Any participant experiences a potentially life-threatening AE, Grade 4 AE or death assessed as related to Study Treatment;
- Any report of anaphylaxis of Grade 3 or greater assessed as related to Study Treatment.

Any SAE or death assessed as related to Study Treatment will lead to an immediate halt of study enrollment and Study Treatments, until the event has been investigated.

8.3.3 Unblinding

The Phase IIa portion of the study will be unblinded at study visit 4 and subjects informed of their treatment status. Subjects assigned to the placebo group may elect to receive vaccine. Regardless of later vaccination status, all subjects will remain in study for safety evaluations.

In the Phase IIa study, all subjects, including those who were assigned to a placebo control group after unblinding, but subjects assigned to placebo who chose not to receive GLS-5310, will be followed for a year from study entry.

Treatment assignments through to the post-vaccination visit (Visit #4) should be maintained as blinded unless unblinding is considered critical to the care and well-being of the subject and that knowledge of the treatment assignment will affect medical management and medical decision making. Unblinding prior to visit #4 should occur following discussion with Sponsor Medical Monitor. However, emergency unblinding can occur if the Investigator deems that such a delay would unduly harm the subject and that knowledge of the treatment assignment is a critical factor in medical decision making versus discontinuation or temporary discontinuation of a study drug until discussion with the Medical Monitor. In the case of unblinding, the Investigator is not required to inform the Sponsor of treatment assignment. Unblinded treatment assignment should be made known only to those who require such information as part of medical decision making and for those involved in Safety reporting to Health Authorities and/or the relevant IRB or local oversight body. In addition, the immunogenicity assay staff must remain blinded until the assay is complete.

Treatment assignments for immunologic measurement should be maintained as feasible throughout the study.

The Investigational Pharmacy at each site will maintain a listing of treatment assignments and will provide a mechanism for unblinding in emergency situations.

After unblinding, collect safety and efficacy results as much as possible even if you are not in the GLS-5310 vaccination group.

9. EVALUATION OF IMMUNE RESPONSES

9.1 Efficacy Parameters

- 1) Determine of GMT and seroconversion rate of SARS-CoV-2 Spike and ORF3a protein specific binding antibody responses induced by GLS-5310 relative to treatment arm(Endpoint titer of binding antibody in serum at each timepoint)

- 2) Determine of GMT and positive responder rate of the neutralizing antibody response induced by GLS-5310(plaque-reduction neutralizing titer in serum at each timepoint)
- 3) Determine the positive responder rate of T cell responses induced by GLS-5310(Antigen-specific interferon gamma (IFN- γ) secretion T-cell response in PBMC at each timepoint)

9.2 Immunogenicity assessments

9.2.1 SARS-CoV-2 Binding ELISA

Standardized ELISA assays will be performed to measure the anti-SARS-CoV-2 S and ORF3a binding antibody responses. Samples will be scored as positive if the average optical density (OD) is greater than 0.10 absorbance units and greater than the average OD before immunization plus 2.5 times the standard deviation (SD) of the OD before immunization at the same dilution. Results will be presented as the geometric mean titer (GMT) of the antibody titer, end-point titer, i.e. the last dilution where the OD value is above the calculated threshold.

The definition of seroconversion as a positive response post-baseline at the lowest dilution tested (i.e. and antibody titer that is below 1:100 at baseline and after vaccination positive at or above the 1:100 dilution) assuming that the baseline response would be negative at 1:100. The criteria for the appropriate immunogenicity of the SARS-CoV-2 binding antibody is planned to have a positive response rate of 70% or more in each group at the interim analysis.

9.2.2 SARS-CoV-2 Serum Neutralization

Neutralizing antibodies against SARS-CoV-2 will be performed the geometric mean of the antibody titer (Geometric mean titer, GMT) to determine the 50% neutralizing titer (NT50) using a plaque-reduction neutralizing titer (PRNT) by standard methodology with relevant virus strains and cell lines. Alternately, pseudovirion-based neutralization assays and/or SARS-CoV-2 receptor binding inhibition assays may also be used to determine the breadth of the neutralizing antibody response to vaccination. The criteria for the appropriate immunogenicity of the SARS-CoV-2 neutralizing antibody is planned to have a positive response rate of 70% or more in each group at the interim analysis.

9.2.3 SARS-CoV-2 ELISpot

Cellular immune responses will be assessed by measuring the number of SARS-CoV-2 antigen-specific IFN- γ secreting peripheral blood mononuclear cells (PBMCs) as determined by IFN- γ ELISpot assays. Cell responses to stimulation with SARS-CoV-2 peptides using 15-mer peptides overlapping by 10 amino acids spanning the entire S and ORF3a proteins will be measured and results reported as spot forming units per million cells (SFU/ 10^6 PBMC). Positive response cutoff calculations will include at least a fold-rise from subject-specific baseline SFU/ 10^6 PBMC values, based upon assay optimization criteria. The criteria for the appropriate immunogenicity of the SARS-CoV-2 T cell response is planned to have a positive response rate of 70% or more in each group at the interim analysis.

10. EVALUATION OF EXPLORATORY ENDPOINTS

10.1.1 Phase I Exploratory Endpoints

- 1) Determine binding antibody responses after a single dose of vaccine related to treatment arm (Endpoint titer of binding antibody in serum at each timepoint)
- 2) Determine whether passive transfer of human serum can protect against pulmonary infection from SARS-CoV-2 challenge in an animal infection model (Survival rate, blood and viral load

measurement of major organs, pathological examination of respiratory/lung area, immunogenicity evaluation)

10.1.2 Phase IIa Exploratory Endpoints

- 1) Determine the persistence of immune responses following vaccination with GLS-5310 (Endpoint titer of binding antibody in serum at each timepoint, Antigen-specific interferon gamma (IFN- γ) secretion T-cell response in PBMC at each timepoint, plaque-reduction neutralizing titer in serum at each timepoint)
- 2) Determine the extent of immune boosting for participants who are seropositive at baseline following vaccination with GLS-5310 (Endpoint titer of binding antibody in serum at each timepoint, Antigen-specific interferon gamma (IFN- γ) secretion T-cell response in PBMC at each timepoint, plaque-reduction neutralizing titer in serum at each timepoint)
- 3) Determine the relative immune responses for those who are age 65 years and younger versus those who are age 66 to 85 years

11. STATISTICAL METHODS and CONSIDERATIONS

Prior to analysis a detailed Statistical Analysis Plan (SAP) will be written describing all analyses that will be performed.

11.1 Data Sets to be Analyzed

- The intention to treat population (ITT) includes all participants who sign informed consent.
- The modified intention to treat population (mITT) includes all participants who sign informed consent and who has received at least one administration of study drug. The mITT population will be the primary analysis population for outcomes.
- The safety set (SS) includes all participants who have received at least one dose of study medication. The SS will be the primary group for safety evaluations and outcome. Analysis of immune responses will be performed only for available samples.

Per-protocol (PP) analysis set includes all participants who complete the trial and who receive all vaccinations and have no significant protocol violations. Participants in this sample will be grouped to treatment arms they actually received. This set will be used as a sensitivity analysis to summarize the primary and secondary efficacy outcomes. For secondary and exploratory assessments of antibody and T cell immune responses, denominators will include only those participants who are SARS-CoV-2 seronegative at baseline. Unevaluable samples will not be considered as part of the denominator at relevant time points. For study participants who are seropositive at baseline, separate assessment of antibody and T cell responses will be performed.

The Phase IIa portion of the study will be unblinded at the post-vaccination visit (visit 4) and all persons who were randomized to the placebo arm offered vaccination with GLS-5310. Safety assessments will be determined based on the actual treatment received. Persons randomized to the placebo group who elect vaccination with GLS-5310 will then be considered to cross-over to the vaccination group as of Week 12. Persons randomized to the placebo group, and who decline vaccination will remain as part of the placebo group, regardless of whether such persons receive any other COVID-19 vaccine. Any study participant who receives an approved COVID-19 vaccine will remain as part of the group assignment as above.

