4.4 Discontinuation/Withdrawal of Study Participants

Participants will be considered to have completed the study when he/she completes all scheduled study treatments and follow-up visits. If a participant discontinues the study at any time after enrollment, but prior to the final scheduled study visit, the investigator will make every effort to have the participant complete all assessments. At a minimum, study participants will be encouraged to complete all procedures included in the final study visit should they elect to terminate early. All data collected up to the time of early termination will be used for final analyses except as noted below. Categories of early study termination are defined below:

- Voluntary withdrawal from the study: the participant verbalizes or states in writing their desire to withdraw from the study. Data already collected remains as part of the study.
- Dropout : the participant has a potentially life-threatening adverse event, grade 4 adverse event, or death that is judged to be related to the vaccination of the investigational product, or anaphylaxis of grade 3 or higher that is considered to be related to the vaccination of the investigational product is reported.
- Withdrawal of consent: When the subject makes a verbal or written request to cease participation in the clinical trial and also withdraws consent to the use of all clinical trial data. If the subject agrees to the use of clinical trial data already collected after discussion

with the investigator, the subject is classified as “Stop participating in voluntary clinical trials”.

- Lost to follow-up: the participant terminates, does/will not return to complete study visits and cannot be located, or does not respond to multiple attempts at contact.
- Major protocol violation: the participant failed to adhere to protocol requirements. Such events will be discussed on a case-by-case basis between the Medical Monitor and the site Principal Investigator (PI) to determine whether these events constitute a deviation that requires removal of the participant from the study and/or non-use of study data.
- Adverse event (Adverse Drug Reaction): clinical or laboratory events that in the medical judgement of the investigator are grounds for discontinuation for the best interest of the participant. This includes serious and non-serious adverse events regardless of relation to study drug.
- Death: the participant died.

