11.4 Immune Response Analysis

The study is not designed or powered to determine efficacy of the vaccine. However, immune response to the vaccine may be assessed by responder analysis of the immunogenicity data.

Immunogenicity results will be classified as responder/non-responder and will be analyzed as the frequency of responses for each assay for each treatment arm at each time point at which an assessment is performed. Estimates of proportions and exact 95% binomial CIs and 95% CIs for the differences between the groups will be calculated.

Immunogenicity analysis will be performed in the mITT and PP groups with evaluable immune response data.

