Intention to treat (ITT) will include all participants who sign informed consent.

✓ **Modified Intention to treat (mITT)**

Modified intention to treat (mITT) will include all participants who sign informed consent and who have received at least one administration of investigational product. The mITT will be the primary analysis population for baseline and demographic assessments and efficacy outcomes. All subjects will be summarized based on the treatment group to which they were assigned. Since not all subjects will have evaluable immune response data, analysis of immune responses will be performed only for available samples.

✓ **Safety Set (SS)**

Safety Set (SS) will include all mITT participants. The SS will be the primary population for summary and analysis of safety assessments. All subjects will be summarized based on the treatments that actually received.

✓ **Per-Protocol Set (PPS)**

Per-Protocol Set (PPS) will include all mITT participants who complete the trial by receiving all

CONFIDENTIAL

vaccinations and have no significant protocol violations. This set will be used as a sensitivity analysis to summarize the primary and secondary response outcomes. For secondary and exploratory assessments of antibody and T cell immune responses, denominators will include only those participants who are SARS-CoV-2 seronegative at baseline. Unevaluable samples will not be considered as part of the denominator at relevant time points.

Protocol violations that can be excluded from the analysis group include the following and are defined according to the analysis population's definition of 'SOP 0406'.

- Participants who have never been vaccinated with all vaccinations
- Positive for SARS-CoV-2 serum test at Baseline
- Inclusion/Exclusion criteria violation
- Contraindicated drug administration
- Randomization errors
- Vaccination errors
- No blood draw for immunogenicity assessment

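### The protocol makes per-protocol membership at Visit 4 depend on completing later follow-up; the SAP words the set differently, does not declare the change, and sets no visit cut-off

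*Protocol*

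**What the plan says.** Protocol 11.1 defines the set as follows: "Per-protocol (PP) analysis set includes all participants who complete the trial and who receive all vaccinations and have no significant protocol violations". It gives the set one role: "This set will be used as a sensitivity analysis to summarize the primary and secondary efficacy outcomes". The main analysis lies elsewhere: "The mITT population will be the primary analysis population for outcomes". Protocol 11.4 adds: "Immunogenicity analysis will be performed in the mITT and PP groups with evaluable immune response data".

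Protocol 4.4 says what completion means: "Participants will be considered to have completed the study when he/she completes all scheduled study treatments and follow-up visits". It names no week. The end point comes from the schedules, where Visit 8 is at Week 48 in Tables S2 and S3. The synopsis gives a total of 60 weeks for placebo participants who take GLS-5310 after unblinding at Visit 4.

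SAP 6 words the set differently: "Per-Protocol Set (PPS) will include all mITT participants who complete the trial by receiving all", and the sentence runs on over the page break to the vaccinations, followed by the condition of no significant violations. Its list of excluding violations begins with "Participants who have never been vaccinated with all vaccinations". It then covers a positive baseline SARS-CoV-2 test, eligibility, contraindicated drugs, randomisation errors, vaccination errors, and absence of an immunogenicity blood draw. Missed late visits and early withdrawal are not on the list. SAP 12, which records changes from the protocol's analyses, does not mention the PP definition.

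**The concern.** The Visit 4 sample is taken four weeks after the second dose. A PP analysis at that visit should ask whether the result holds among people who followed the regimen up to then. Under the protocol wording it also asks whether they stayed for the rest of the trial. In Phase IIa that later period begins when participants learn their assignment. Placebo participants are then offered GLS-5310, and protocol 1.4 and 11.1 foresee that some participants will receive other COVID-19 vaccines. Reasons for staying or leaving may therefore differ by arm.

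This is the only sensitivity set that the plan names for the primary and secondary responses. If later retention selects it, agreement or disagreement with the main analysis says little about adherence to the regimen. With two definitions in force and no declared change, the analyst must also choose between them, possibly after results are known.

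**Working it through.** **1. How long after Visit 4 membership stays open under the protocol wording.** Visit 4 is at Week 12 on the 0-8 schedule (Table S2) and Week 16 in arm 1c (Table S3).
- 0-8 schedule, no crossover: 48 − 12 = 36 weeks.
- Arm 1c: 48 − 16 = 32 weeks.
- Placebo participant who crosses over at Week 12: 12 + 48 = 60 weeks, which reproduces the synopsis figure; 60 − 12 = 48 weeks.

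Phase I is open-label and has no crossover, so the point about unblinding concerns Phase IIa only.

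**2. Whether anyone would qualify at a Visit 4 interim under the protocol wording.** Inputs: recruitment of about 5 months (synopsis), taken as 5 × 30.4 = 152 days; latest Visit 4 at day 87 (0-8) or day 115 (0-12), and earliest Visit 8 at day 329 (SAP 8.3, Tables 2 and 3).
- 0-8: when the last participant reaches Visit 4, the first is at day 87 + 152 = 239, short of 329.
- 0-12: 115 + 152 = 267, also short of 329.
- For one completer to exist, recruitment would have to spread over 329 − 87 = 242 days (34.6 weeks) or 329 − 115 = 214 days (30.6 weeks).

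So the set would be empty if PP were run at those interims under the protocol wording.

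**3. The same questions under the SAP wording.** If receiving all vaccinations is what completes the trial, the condition is met at Week 8 (Week 12 in arm 1c). Membership then does not depend on late visits, and the set is not empty at Visit 4. Four things remain unsettled:
- SAP 9.1 tabulates study completion separately from status at Visit 4, so the SAP does not use completion consistently to mean vaccination.
- The blood-draw exclusion names no visit, while samples are also due at Visits 5 to 8. A missed later draw could be read as removing someone from the Visit 4 analysis.
- The contraindicated-drug exclusion has no end date. Protocol 5.3.2 runs its prohibition to 4 weeks after the last vaccination: Week 8 + 4 = 12 for the randomised series. If crossover doses count, it runs to Week 12 + 8 + 4 = 24 for crossed-over placebo participants.
- Neither document says whether the Table S4 series counts towards all vaccinations.

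**4. Possible size under the protocol wording.** The documents give no dropout rate, so every loss below is an assumption. With true Visit 4 response rate p, and fractions a of responders and b of non-responders lost later, the PP rate is p(1 − a) / [p(1 − a) + (1 − p)(1 − b)].
- p = 80%, a = b = 10%: 0.72 / (0.72 + 0.18) = 80.0%.
- p = 80%, a = 10%, b = 30%: 0.72 / (0.72 + 0.14) = 83.7%.
- p = 80%, a = 20%, b = 5%: 0.64 / (0.64 + 0.19) = 77.1%.
- p = 70%, a = 10%, b = 30%: 0.63 / (0.63 + 0.21) = 75.0%.

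Precision, using the Wald 95% half-width 1.96 × √(0.8 × 0.2/n₁ + 0.1 × 0.9/n₂) for assumed response rates of 80% and 10%: the planned 80 vaccine and 40 placebo participants give 12.8 points. Losing an assumed 20% and 30% leaves 64 and 28, which gives 14.8 points.

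**The case against.** The strongest reply is that the SAP is the document that describes the analyses to be performed (opening of protocol 11), and that its wording removes the dependence on late follow-up. That is a fair reading, and it rules out saying flatly that the PP set is conditioned on Week 48. It does not settle the matter: the SAP still speaks of completing the trial, does not declare a departure from the protocol, and leaves its exclusions without a visit cut-off.

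A reader might go further than the documents allow in three ways:
- *That the interim analyses fail because the PP set is empty.* The interim texts (protocol 3.1 and 11.5, SAP 4.1) name safety and antibody response, and none assigns PP to an interim or a decision. Protocol 11.4 is general. Emptiness follows only if PP is run then under the protocol wording.
- *That a placebo participant who misses the second crossover dose is removed from the Week 12 comparator.* No text says so. The synopsis keeps crossed-over participants separate from the randomised vaccine group, and SAP 10.1 gives them their own exposure group. The documents are silent on their PP status, which calls for a rule but does not show an exclusion.
- *That the PP response rate will be inflated.* The upward shifts require non-responders to leave more often than responders. Visit 4 informs participants of their treatment assignment, and no text says they learn their antibody results. Equal losses give no shift, and the opposite pattern gives a downward one.

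It is also fair to say that the SAP calls the trial exploratory and descriptive, and that endpoints are assessed at each time point, with Visit 4 not singled out as the main one.

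**Conclusion.** The point holds as a conflict between two definitions, with a defect in the protocol's version. Protocol 11.1 read with 4.4 makes Visit 4 membership depend on 32 to 48 later weeks. SAP 6 can be read as dropping that dependence, but SAP 12 does not say so, and crossover doses and later exclusions are left open. The consequence is limited to the sensitivity analysis; the primary set is unaffected and no interim decision rests on PP.

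The size of any bias cannot be estimated from the documents. The assumed losses move an 80% rate by between −2.9 and +3.7 points and widen the interval by about 2 points; they show what is possible, not what is likely. The empty-set result rests on the protocol wording and on recruitment of about 5 months. The change is worth making because it is nearly free and removes a choice that might otherwise be made with results in view.

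**What to change.** Use one definition in protocol 11.1 and SAP 6. Remove the trial-completion condition and set PP membership separately for each visit. A participant belongs at a visit if the allocated doses scheduled before that visit's sample were received, the sample at that visit is evaluable, and no significant violation occurred up to that visit. Apply the same cut-off to the blood-draw and contraindicated-drug exclusions.

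State that doses received or missed, and other events, after the Visit 4 crossover do not alter Visit 4 membership. For Phase IIa, derive Visit 4 membership only from the data that SAP 4.1 says were locked before unblinding. List the change in SAP 12.

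The cost is a few sentences and PP counts that vary by visit in the analysis-set table; no new data are needed. One limit remains: SAP 4.1 reports the Phase IIa interim as already performed, so the rule cannot now be presented as fixed before unblinding. Restricting it to the locked data keeps later events out of the membership decision, and SAP 12 should give the date on which the rule was adopted.
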